## 9.8 Plans for analyzing the exploratory objectives:

- 9.8.1 Aim 2: To assess the potential effect of known and potential moderators on treatment effectiveness between the two arms.

We will export the moderator effects on treatment effectiveness.

There are 2 outcomes collected at 2 time points and 2 outcomes at 1 time point:

- Biochemically-verified 7-day point prevalence abstinence at 3- and 6-months follow-up
- Self-reported cigarette abstinence at 3- and 6-months follow-up
- Continuous abstinence at 6 months (no self-reported smoking since last survey point)
- Sustained abstinence at 6 months (biochemically-verified abstinence at 3 and 6 months)

The moderators of primary interest are:

- Sociodemographics: Sex, age, marital status, race/ethnicity, education level, financial burden, health insurance, internet and smartphone access and modality
- Smoking history: Years smoked, daily smoking rate, other tobacco/nicotine use (e.g., cigars, cigarettes), current/past use of tobacco treatments, nicotine dependence (2-item “Heaviness of Smoking Index” from the FTND)
- Cancer variables: Cancer type, cancer stage, treatment, and days since diagnosis
- Site characteristics:
  - Site, geographic location, clinic volume,
  - baseline organizational readiness (9-item survey for readiness to implement NCCN Guidelines for Smoking Cessation using Weiner’s Organizational Readiness for Implementing Change (ORIC) survey)
  - site usual care (recorded on the 2017 landscape survey)

Additional moderators to be explored:

- Medical history: ECOG Performance Status, alcohol use (3 items from the AUDIT-C)

- Quality of life/emotions: Emotional distress, coping, anxiety, depression
- Cancer and smoking beliefs: Stigma, quit motivation, self-efficacy to quit, importance of quitting, perceived benefits of quitting smoking, quit-smoking medication beliefs
- Physical symptoms: Cravings
- Environmental influences: Level of second-hand smoke exposure, perceived social support, perceived provider support

For each of the 6, we will test the effects of these moderators listed above on the outcomes. We test the effects of these moderators in logistic regression models to determine their association with tobacco abstinence. Once a parsimonious multivariate model is developed, treatment arm will be included to test for the effect of the intervention on the moderators. Interactions between the treatment arm and the moderators will assess the relationship between the moderators and the treatment group on the effectiveness outcomes.

Also, GEE will be used to look at longitudinal models.

Multiple comparisons will be accounted for by considering Bonferroni adjustments.

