
### 1.2.1 Current R01 preliminary findings (Smokefree Support Study 1).

The proposed study was informed by the recently completed RCT which Drs. [name] and [name] conducted at MGH and Memorial Sloan Kettering (MSK) to assess integration of an Intensive Treatment (IT; 11 sessions of motivational counseling, in-person and phone, plus choice of FDA-approved medication) versus MSK's usual care with recently diagnosed cancer patients (4 sessions of MI counseling plus FDA-approved medication advice). Among patients who are potentially eligible based on chart screen, approximately one-third enrolled; among known eligible smokers who agreed to be screened, 70% enrolled. Based on preliminary analyses as of February 2018, 303 patients were enrolled and randomized to a treatment arm (56%

female, mean age = 58; 82% white, non-Hispanic; 10 % Black; 5.0% Hispanic). This includes patients diagnosed with thoracic, head and neck, GI, GU, breast, lymphoma, melanoma, and ob/gyn cancers. Using intention-to-treat analyses counting non-responders as "smokers" (86% 6-month survey response rate and 87% cotinine validation response rate), cotinine validated 6-month abstinence rates are 19% in the Standard Care group and 33% in the Intensive Treatment group ( $p < .02$ ). Using intention-to-treat, 57% of Intervention Treatment group participants were adherent to sustained counseling (> 7 sessions), which was associated with increased 6-month quit rates ( $p < .0001$ ). These data support preliminary effectiveness of the proposed intervention treatment.

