### 5.2 Enhanced Usual Care (EUC) (Arm A)

The EUC reflects the NCCN Smoking Cessation Guideline recommendations and mirrors what is often delivered at cancer centers and community settings: assessment of smoking status, provision of quitting advice, and referral to the national NCI Smokers' Quitline for free counseling. Some participating NCORP community sites might provide additional tobacco treatment, which we will assess and document as well.

All participants randomized to EUC will have received the assessment of smoking status and provision of quitting advice through the screening and recruitment (virtual clinician referral) process, and will additionally be referred to the NCI Smoking Quitline (smokefree.gov). Referrals will be sent via email by EASEE PRO automatically upon randomization to the EUC arm see

supplemental Appendix P). Referrals will also be sent via mailed letter (see EUC Referral Letter Supplemental Appendix Z1A) by the MGH study staff to the address provided by EUC participants.

On an ongoing basis, the NCI Quitline will provide reports on participant engagement (date and duration of Quitline call) with quitline services. This interaction will be documented in Rave.

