**6.3.1 NCORP Site Characteristics:**

At the time of site registration, the CCDR Lead or their designee(s) will complete the site rostering survey. This survey requests that applicable CTEP IDs be grouped into larger practice groups with shared providers, populations served and services offered. For each practice group, the CCDR Lead or their designee(s) will complete items regarding practice characteristics including safety net designation, minority/underserved NCORP status, geographic site location, practice volume, provider mix and ownership, and tobacco cessation services that are available for patients treated at each practice group.

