7.6 Data collection schedule for site staff (surveys)

	Baseline	12 Month	36 Month
Site Staff			
Adoption	X	X	X
Appropriateness	X	X	X
Treatment fidelity	X	X	X
Cost		X	X
Feasibility	X	X	X
Site characteristics	X	X	X
Penetration/reach		X	X
Sustainability	X	X	X

Rev. Add3

. Site staff must complete baseline survey prior to first patient enrollment

Rev. Add4

. CCDR Leads will complete Site Characteristics at approximately 12 and 36 Month Follow-up (Appendices E and F)

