#### 9.8.2

Aim 3: To assess the processes of implementation and dissemination (acceptability, adoption, appropriateness, treatment fidelity, cost effectiveness, penetration/reach, and sustainability) of our intervention at community oncology sites.

To gain an initial understanding of implementation processes, for Aim 3 we will follow Proctor and colleagues' recommended taxonomy for measurement of implementation outcomes. Specifically, we will measure acceptability (satisfaction with content/delivery), adoption (program uptake), appropriateness (relevance), cost, and treatment fidelity/adaptation and penetration (reach) and sustainability. These implementation outcomes will be assessed with mixed methods using qualitative and quantitative data to be collected from patients, tobacco treatment counselors, NCORP oncology PIs and provider clinicians/staff, and EHR documentation.

We will use descriptive statistics to summarize implementation outcomes (Acceptability, Adoption, Appropriateness, Fidelity, Cost, Penetration and Sustainability) and conduct treatment group comparisons (i.e., Acceptability).

We will explore organizational readiness and site level engagement using existing quantitative and qualitative data respectively. In order to examine the generalizability of the study findings to the full NCORP network of cancer care delivery sites, we will use the most recent (2017) existing NCORP Landscape data to conduct preliminary analyses comparing participating and nonparticipating sites on relevant site characteristics.

	
9.8.2.1 Acceptability
 
Satisfaction with various aspects of the tobacco treatment program will be evaluated through participant survey responses and post-treatment interviews with a subset of patient participants. Patient Surveys. At the 6-month surveys, participant satisfaction will be assessed:
 

1 To what extent has the tobacco treatment program met your needs?;

2 How satisfied were you with the smoking cessation assistance received?;

3. How helpful was the smoking cessation assistance?;

4. Would you recommend this program?

 
Proportions of participants answering these questions will be compared between the arms using chi-squared tests.

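### The site usual care moderator in 9.8.1 is taken from a 2017 survey, although the trial records cessation services per practice group at registration; it may be out of date for some sites

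*Combined protocol and SAP*

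**What the plan says.** Section 2.4 lists site usual care among the moderators of primary interest and gives no source. Section 9.8.1 repeats the list and adds the source: "site usual care (recorded on the 2017 landscape survey". This is the only place where the source is fixed.

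The trial also collects its own record. Section 6.3.1 states: "At the time of site registration, the CCDR Lead or their designee(s) will complete the site rostering survey". In that survey "applicable CTEP IDs be grouped into larger practice groups with shared providers", and for each group the site reports, among other things, the "tobacco cessation services that are available for patients treated at each practice group". A footnote to the schedule in 7.6 adds that "CCDR Leads will complete Site Characteristics at approximately 12 and 36 Month Follow-up". Section 5.2 makes a related promise for the control arm: "Some participating NCORP community sites might provide additional tobacco treatment, which we will assess and document as well".

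The 2017 data have a second use. In 9.8.2, for generalizability, "we will use the most recent (2017) existing NCORP Landscape data to conduct preliminary analyses" that compare participating with nonparticipating sites.

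**The concern.** Usual care is the background against which the control arm is measured. Whether the virtual intervention adds less where a site already offers cessation services is a natural Aim 2 question, and its answer depends on knowing what each site offered when its patients were enrolled.

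The plan ties that moderator to an external record made before any site could register, and leaves unused a pre-enrolment record that the trial itself obtains. The plan also treats site practice as something that can change: 9.8.2.2 tests for change in tobacco treatment delivery between the baseline, 12-month and 36-month staff surveys. If services changed at some sites after 2017, patients there carry the wrong label and the arm-by-usual-care interaction is estimated from mixed groups.

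**Working it through.** **Order of events.** The protocol cites its own earlier trial as follows: "Based on preliminary analyses as of February 2018, 303 patients were enrolled". A site registering under this text therefore does so after 2017. Section 4 requires an approved site registration before a patient is enrolled, so the rostering survey is also a pre-enrolment measure and is the closer of the two to enrolment. Section 7.2 places the 36-month staff survey after the last patient is enrolled, so accrual at a site may run to about three years past its baseline. The 2017 record would be older still for those late patients.

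**Why the two uses of the 2017 data differ.** The comparison in 9.8.2 includes nonparticipating sites, which complete no trial survey, so existing data are needed there. The moderator analysis uses participating sites only, and each of these completes the rostering survey. The reason for the 2017 source in 9.8.2 does not carry over to 9.8.1.

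**Direction of the error.** Randomization is stratified within site (4.6). A wrong site label therefore applies equally to both arms at that site, and the error is expected to be non-differential by arm. For a two-level moderator this attenuates the interaction on average.

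**Size (hypothetical).** The plan gives no effect, power or error rate for this moderator, so there is no figure to reproduce. Assume a yes/no moderator, a true share q of patients at sites with services, and the same misclassification rate m in both directions. On the risk-difference scale:

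- fraction of the interaction retained = PPV − (1 − NPV)
- PPV = q(1 − m) / P and 1 − NPV = qm / (1 − P), where P = q(1 − m) + (1 − q)m is the share labelled as having services
- at q = 0.5 this reduces to 1 − 2m

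| m (assumed) | retained, q = 0.5 | retained, q = 0.3 or 0.7 |
|---|---|---|
| 0% | 1.00 | 1.00 |
| 10% | 0.80 | 0.75 |
| 20% | 0.60 | 0.54 |
| 30% | 0.40 | 0.35 |

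Example at q = 0.3, m = 10%: P = 0.27 + 0.07 = 0.34; 0.27/0.34 − 0.03/0.66 = 0.794 − 0.045 = 0.75. The plan fits logistic models, so factors on the log-odds scale will differ somewhat.

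**Effect on power (hypothetical).** Take the design rates in 9.1 (15% and 32%) and the 280 participants in 9.2.1. That design reproduces: (0.32×0.68 + 0.15×0.85)(2.576 + 0.842)²/0.17² = 139.5, so 140 per arm. Now assume control abstinence of 25% with services and 5% without (mean 15%), 32% in the intervention arm everywhere, and 70 patients in each of the four cells. The true interaction is 20 percentage points. With no misclassification:

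- SE = √[(0.25×0.75 + 0.05×0.95 + 2×0.32×0.68)/70] = 0.098
- power at two-sided 0.05 = Φ(0.20/0.098 − 1.96) = 53%

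The same calculation with mixed groups gives:

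| m (assumed) | interaction | power |
|---|---|---|
| 0% | 0.20 | 53% |
| 10% | 0.16 | 37% |
| 20% | 0.12 | 23% |
| 30% | 0.08 | 12% |

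**The case against.** **Staleness is not shown.** A reader might infer that the moderator is in fact out of date and its interaction in fact diluted. The documents do not support that. They report no change in services at any participating site after 2017, and they do not say at what organisational level the landscape survey recorded usual care, so it cannot be called coarser. If the 2017 record still agrees with the registration record, the loss is zero. This objection stands and limits the point to a risk.

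**Attenuation is an average result.** The plan does not say that usual care is coded yes/no, and with several categories attenuation is not assured. Section 3.1 foresees a minimum of 11 sites, so one wrong site may be 1/11 = 9% of them, and misplacing one or two particular sites can move a single estimate either way. This also stands.

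**Availability is not delivery.** The rostering item asks what is offered. Without the landscape items, nobody can show that the newer item measures the same thing or measures it better. This stands as a cost of the change. It does not justify the older source, for which the plan gives no rationale.

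**Other data cover usual care.** Site itself is a listed moderator, perceived provider support is an additional one, and 9.8.2.3 and 9.8.2.4 describe site usual care and its use. These reduce the loss, but none of them is the named moderator.

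**The test is weak anyway.** Section 9.8.1 says Bonferroni adjustment will be considered. I count 22 moderators of primary interest; at 0.05/22 = 0.0023 the illustrative 53% falls to about 16% even with perfect labels. That is true, and it is why the point is minor.

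**Later updates look attractive but are unsuitable.** A reader might infer that the 12- and 36-month values would be better still because they are newer. They are measured after enrolment starts and may reflect trial participation, and the forms are not available here to confirm that they repeat the services item.

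**Conclusion.** The point holds as a minor improvement to an exploratory analysis. It is established that 9.8.1 is the only text giving a source for this moderator, that the source predates registration and enrolment, and that a newer pre-enrolment measure per practice group is planned and left out of Aim 2.

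It is not established that any site is misclassified. If some are, the expected direction is attenuation: 0%, 20%, 40% or 60% of the interaction at misclassification of 0%, 10%, 20% or 30%. These figures assume a 50/50 binary moderator with symmetric error unrelated to arm; the true rate is not in the documents. Nothing here touches the primary comparison, its 0.01 significance level or the total of 308 patients.

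**What to change.** In 9.8.1, replace the reference to the 2017 survey with a definition of site usual care as the tobacco cessation services available in the patient's practice group, as recorded in the site rostering survey at registration (6.3.1), and state how those services will be coded. Keep the 2017 landscape value for the participating-versus-nonparticipating comparison in 9.8.2, and repeat the moderator analysis with it as a sensitivity analysis. Setting the two records side by side would also show how often they agree, which is the figure missing above. Do not use the 12- and 36-month updates as moderators. If the 2017 source is deliberate, give the reason in 9.8.1.

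Cost: one phrase in the plan and no new data collection. Patients must be linked to practice groups; since the groups are built from CTEP IDs and the enrolling institution is recorded at registration, a lookup table should suffice. The measure will describe services on offer, not services received, and should be reported as such.

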### 3. Participant Selection

#### 3.1 Selection of NCORP Site Staff Participants

In order to achieve Aim 3, we will enroll a subset of staff (n=approximately 110) from a minimum of 11 participating NCORP sites. We are seeking to elicit implementation process perspectives from key stakeholders (clinicians and research administration staff) who would most likely be instrumental in making tobacco use assessment and treatment routine part of cancer care. Guided by his/her knowledge of key stakeholders' roles and responsibilities, the Cancer Care Delivery Research (CCDR) Leader and site PI from each participating site will be responsible for identifying approximately 10 multidisciplinary staff members to complete brief (approximately 15 minute) surveys and participate in focus group interviews (approximately 45-60 minutes). The focus group interview will be conducted approximately 24-36 months after site activation, upon the completion of 36-month follow-up surveys by the site. Although specific site staff participant composition will vary somewhat by site, we envision participation of the CCDR Leader, the Site PI, 2-3 oncology nurses, 2-3 additional medical oncologists and 2-3 additional staff members.

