## 9. Statistical Considerations

### 9.1 Estimated Effect Size

Based on our current trial preliminary findings (Preliminary Studies) and previous trial with low SES smokers, we conservatively estimate 7-day point-prevalence tobacco abstinence at 6-month follow-up will be 15% for the standard care group and 32% for the intervention group. This estimate is based on our current trial, which has a higher intensity control group.

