### 9.2 Power calculation:

#### 9.2.1 Aim 1. Primary effectiveness outcome.

The study will have 80% power to detect a 17% difference in 7-day point-prevalence tobacco abstinence with a two-sided significance level of 0.01 with 280 participants.

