#### **Numeric Results for Testing Two Proportions using the Z-Test with Unpooled Variance**

H0:  $P1 - P2 = 0$ . H1:  $P1 - P2 = D1 \neq 0$ .

Target	Actual	Diff						
		Power	Power* N1	N2	N	P1	P2	D1
0.80	0.80400	117	117	234	0.2700	0.1000	0.1700	0.0100
0.90	0.90042	148	148	296	0.2700	0.1000	0.1700	0.0100
0.80	0.80014	78	78	156	0.2700	0.1000	0.1700	0.0500
0.90	0.90167	105	105	210	0.2700	0.1000	0.1700	0.0500
0.80	0.80045	126	126	252	0.2900	0.1200	0.1700	0.0100
0.90	0.90130	161	161	322	0.2900	0.1200	0.1700	0.0100
0.80	0.80185	85	85	170	0.2900	0.1200	0.1700	0.0500
0.90	0.90186	114	114	228	0.2900	0.1200	0.1700	0.0500
0.80	0.80184	140	140	280	0.3200	0.1500	0.1700	0.0100
0.90	0.90061	178	178	356	0.3200	0.1500	0.1700	0.0100
0.80	0.80115	94	94	188	0.3200	0.1500	0.1700	0.0500
0.90	0.90119	126	126	252	0.3200	0.1500	0.1700	0.0500
0.80	0.80095	148	148	296	0.3400	0.1700	0.1700	0.0100
0.90	0.90146	189	189	378	0.3400	0.1700	0.1700	0.0100
0.80	0.80289	100	100	200	0.3400	0.1700	0.1700	0.0500
0.90	0.90024	133	133	266	0.3400	0.1700	0.1700	0.0500
0.80	0.80043	159	159	318	0.3700	0.2000	0.1700	0.0100
0.90	0.90101	203	203	406	0.3700	0.2000	0.1700	0.0100
0.80	0.80088	107	107	214	0.3700	0.2000	0.1700	0.0500
0.90	0.90015	143	143	286	0.3700	0.2000	0.1700	0.0500

\* Power was computed using the normal approximation method.

- 9.2.2 Aim 1. Secondary effectiveness outcome 1.  
For biochemically-confirmed 7-day point prevalence abstinence at 3-months, with a sample size of 140 in each arm then smallest detectable difference will be 18% with 80% power and a Bonferroni corrected alpha of 0.002 using and an estimated control rate of 20%.
- 9.2.3 Aim 1. Secondary effectiveness outcome 2.  
For self-reported 7-day point prevalence abstinence at 6-months, with a sample size of 140 in each arm then smallest detectable difference will be 22% with 80% power and a Bonferroni corrected alpha of 0.002 using and an estimated control rate of 31%.
- 9.2.4 Aim 1. Secondary effectiveness outcome 3.  
For self-reported 7-day point prevalence abstinence at 3-months, with a sample size of 140 in each arm then smallest detectable difference will be 22% with 80% power and a Bonferroni corrected alpha of 0.002 using and an estimated control rate of 28%.
- 9.2.5 Aim 1. Secondary effectiveness outcome 4.  

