For continuous abstinence, with a sample size of 140 in each arm then smallest detectable difference will be 21% with 80% power and a Bonferroni corrected alpha of 0.002 using and an estimated control rate of 20%.
- 9.2.6 Aim 1. Secondary effectiveness outcome 5.  
For sustained abstinence, with a sample size of 140 in each arm then smallest detectable difference will be 19% with 80% power and a Bonferroni corrected alpha of 0.002 using and an estimated control rate of 13%.
- 9.3 Estimate of drop-outs/loss to follow-up:  
We estimate that 10% of participants will die within 6-months of enrollment, so an additional 10% (n=28) will be recruited.
- 9.4 Total Sample size:  
308 patient participants.
- 9.5 Plans for handling missing data:  
At the outset, we will examine the frequency distributions of all variables. Data from all sites will be pooled for analysis, after confirming there is no significant heterogeneity among sites or adjusting as needed. We will compare the baseline characteristics to assess whether randomization distributed covariates evenly. Outcome analyses will be intent-to-treat; we will classify participants who are lost to follow-up and those who do not provide a saliva or an expired air sample as current smokers. We will determine whether there is differential dropout in the groups and consider developing probability-of-completion weights to obtain unbiased estimates of treatment effect. We will assess whether data are missing at random. We will perform sensitivity analysis using: 1) a complete case analysis and 2) multiple imputation for missing data.

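### Site-level moderators are tested in patient-level logistic models with no allowance for clustering by site, so their main-effect tests reject too often if quit rates differ between sites.

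*Combined protocol and SAP*

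**What the plan says.** Section 9.8.1 (Aim 2) names site characteristics as moderators of primary interest, beginning with "Site, geographic location, clinic volume" and continuing with baseline organizational readiness and site usual care. For each of six abstinence outcomes the procedure is: "We test the effects of these moderators in logistic regression models to determine their association with tobacco abstinence". A reduced multivariable model is built, treatment arm is added, and arm-by-moderator interactions are then examined. GEE is mentioned for longitudinal models only, and section 9.7 describes its clustering as repeated measures within a person. Bonferroni adjustment is to be considered, with no number of tests or alpha given.

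Four other places bear on site:
- Section 3.1 plans to enrol staff "from a minimum of 11 participating NCORP sites".
- Section 4.6 stratifies randomization within site.
- Section 5.1.2 sets a goal of 25 patients per subcomponent site and allows other targets.
- Section 9.5 pools the sites if no significant heterogeneity is found and otherwise adjusts where necessary, without giving a test, threshold or method.

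**The concern.** A characteristic that takes one value per site carries information from the number of sites, not the number of patients. An ordinary logistic model on about 300 patients treats them all as independent evidence about, say, clinic volume. If sites differ in quit rate for any other reason, that variation is left out of the standard error.

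Two things are at stake. The association tests could report readiness, volume, location or usual care as related to abstinence when they are not. And because these associations drive the building of the reduced model, falsely significant site factors can be carried into the model in which arm and the interactions are then examined.

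A separate difficulty is that Site is itself a listed moderator. As a fixed interaction with arm it splits the data into cells of about 12 to 14 patients, some of which may contain no quits.

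**Working it through.** **1. The plan's own figure.** Section 9.1 assumes abstinence "will be 15% for the standard care group and 32% for the intervention group", and section 9.2.1 sets 80% power "with a two-sided significance level of 0.01 with 280 participants". With the unpooled-variance formula used in 9.2.1:

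n per arm = (2.576 + 0.842)² × (0.32×0.68 + 0.15×0.85) / 0.17² = 139.46, so 140 per arm and 280 in total. Power at 140 per arm is 0.8018. Adding 28 (9.3) gives 308.

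The figure reproduces. It concerns the primary comparison only; no figure is given for Aim 2.

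**2. Number of units (assumption).** 308/25 = 12.3, and 308/12 = 25.7 patients per site. The documents fix only a minimum of 11. Section 6.3.1 records volume and location per practice group, so the number of units could be larger.

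**3. Design effect for a characteristic constant within site.** DE = 1 + (m − 1) × ICC; effective N = 308/DE; actual error = 2 × [1 − Φ(1.96/√DE)]. The ICC (response scale) is an assumption; m = 25.7.

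| ICC | DE | Effective N | Actual error at nominal 5% | At nominal 1% |
|---|---|---|---|---|
| 0 | 1.00 | 308 | 5% | 1% |
| 0.01 | 1.25 | 247 | 7.9% | 2.1% |
| 0.02 | 1.49 | 206 | 10.9% | 3.5% |
| 0.05 | 2.23 | 138 | 19.0% | 8.5% |

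**4. Simulation of the main-effect test.** 2,000 to 4,000 trials per setting, 11 to 12 near-equal sites of 26 to 28 patients, 15% versus 32% abstinence, a site characteristic with no true effect, ordinary logistic Wald test at nominal 5%. The between-site SD on the log-odds scale is an assumption. The lower end of each range mostly reflects variation in intercepts only, the upper end variation in intercepts and treatment slopes.

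| Between-site SD | Latent ICC = SD²/(SD² + π²/3) | Rejection rate |
|---|---|---|
| 0 | 0 | about 5% |
| 0.2 | 0.012 | 7-9% |
| 0.3 | 0.027 | 8-11.5% |
| 0.5 | 0.071 | 15-21% |

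At nominal 1%, with intercepts and slopes varying, the rates are 3.4-3.6% (SD 0.3) and about 9% (SD 0.5). A regression of site rates on the characteristic stayed at about 4-6% at nominal 5% throughout. With about 25 units of 12 patients, the patient-level test rejects roughly 6-12% of the time for SD 0.2 to 0.5.

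The latent ICC here and the response-scale ICC in step 3 are not interchangeable: a latent ICC of 0.05 gave 12.5% in simulation.

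**5. Interaction with arm.** With no treatment-by-site variation the patient-level test rejected 4.1-5.4% of the time at every ICC tried. With a slope SD of 0.3 to 0.5 it rejected about 5-8%, and with a slope SD of 0.6 it rejected 9.0%.

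**6. Does the section 9.5 check help?** Taking it as a 5% chi-square test across 12 sites, its power is about 8%, 14% and 36% at latent ICC 0.01, 0.02 and 0.05. It usually passes when modest clustering is present.

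**7. Site-by-arm cells.** The chance that at least one of k sites has no EUC quits among m EUC patients is 1 − (1 − (1 − p)^m)^k, for (k, m) = (11, 14), (12, 13), (13, 12):

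| Outcome and EUC rate p | Chance of an empty cell |
|---|---|
| Verified, 6 months, 15% (9.1) | 70%, 79%, 86% |
| Verified, 3 months, 20% (9.2.2) | 39% to 60% |
| Self-report, 3 months, 28% (9.2.4) | 11% to 22% |
| Self-report, 6 months, 31% (9.2.3) | 6% to 14% |

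An empty cell gives a non-finite estimate for that site's interaction term.

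**The case against.** The strongest reply is that Aim 2 concerns moderation, which is tested by the interaction. Because randomization is within site, a shared site effect largely cancels there. That stands. A reader might infer that moderator findings generally carry a 7-21% false-positive rate; step 5 does not support this. The larger figures belong to the main-effect tests, which still matter because they select the model.

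Second, the plan is not silent on site: Site is a listed moderator and 9.5 allows adjustment. This is fair as to wording, but a fixed site term is collinear with every characteristic constant within site, so it cannot correct their tests. If adjustment meant a valid site-level analysis after a positive heterogeneity test, overall error would be about 5-6%. Nothing in 9.5 says that it does.

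Third, the size is assumed. That stands. There is no ICC, the site count is inferred, and with no between-site variation the tests are correct.

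Fourth, the analysis is exploratory and Bonferroni may be applied. The first part limits the importance of the point. The second does not repair a wrong standard error: the inflation is about fourfold at 5% and about ninefold at 1% for SD 0.5.

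A reader might also infer that these results flow into the implementation conclusions. Aim 3 has its own descriptive and qualitative analyses in 9.8.2, section 3.1 places the staff data at the level of the site, and no text feeds 9.8.1 results into them.

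**Conclusion.** The point holds for main-effect tests of characteristics that are constant within a site or practice group. Section 9.8.1 gives these tests no protection against clustering, and neither the Site moderator nor 9.5 supplies it. At nominal 5% they reject about 7-21% of the time, given about 12 sites of 26 and a between-site SD of 0.2 to 0.5, and roughly 6-12% given about 25 units of 12.

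The interaction tests are close to nominal unless the treatment effect varies between sites, and then run at about 5-8% for the SDs assumed.

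The fixed Site-by-arm interaction is likely to fail for the verified 6-month outcome (70-86%). It would be wrong to extend that figure to all six outcomes: for self-report it is 6-22%.

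All simulated figures assume near-equal site sizes. The primary result is unaffected.

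**What to change.** In 9.8.1, state that site-level characteristics are analysed at the level at which they are measured. Regress site (or practice-group) abstinence rates on the characteristic for the association, and arm differences in those rates for moderation. Use residual degrees of freedom equal to the number of units minus the number of estimated parameters: 12 − 2 = 10 for one characteristic in 12 sites, fewer if several enter together.

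An alternative is a logistic model with a random site intercept, plus a random arm-by-site slope for interactions if estimable, with the same small-sample degrees of freedom. Only the site-level regression was checked above. About 72 quits are expected (154 × 0.15 + 154 × 0.32), which gives little information on a slope variance, and plain cluster-robust errors are doubtful with 11 or 12 clusters.

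Report the estimated between-site variance of the treatment effect in place of a fixed Site-by-arm interaction. Name the unit (NCORP site or practice group) for each characteristic.

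The cost is SAP wording and a different model call, with no new data. The downside is wider intervals for site-level factors.
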